Benefits Counseling maximizes beneficiaries’ time engaging in work-related activities in the following ways: 1) Providing information about how work might impact receipt of disability payments: One reason people who receive disability payments are disproportionately underemployed is the perception that beneficiaries who work will definitely lose their disability benefits [16, 19]. However, service-connection ratings are based primarily on the *average* impairment in earning capacity, and therefore an individual Veteran is not supposed to be penalized for overcoming a disability by working (38 CFR Section 4.15). There are some exceptions [20] but nevertheless, the best available data are that only about 6% of Veterans who are service connected for PTSD lose these benefits during a ten year period [21]. 2) Amplifying applicants’ existing motivation to engage in work and related-activities, using a Motivational Interviewing approach: Motivation has been associated with success in rehabilitation [22, 23]. Benefits Counseling brings out motivation to work in a non-judgmental, individually-tailored way. 3) Guiding Veterans to available vocational rehabilitation, education, and job-finding services: Veterans applying for disability compensation can benefit from the extensive treatment, rehabilitation, and employment-related resources available to them. There is little in the current VA disability application process that informs patients of vocational rehabilitation opportunities. Results of the 2010 National Survey of Veterans suggested that rehabilitation benefits were underused [24]; only 14.8% of Veteran respondents who applied for disability compensation indicated that they had ever used vocational rehabilitation services. Many who applied for disability benefits but did not use any vocational rehabilitation services indicated reasons that were remediable such as not knowing how to apply and not knowing they were eligible for these services. 4) Encouraging Veterans to seek treatment for psychiatric disorders that are barriers to working. A substantial proportion of Veterans presenting for Compensation examinations have not received VA services before---75.3% in one published study [25]--- making this a valuable opportunity to engage Veterans in treatment and thus reduce health-related barriers to working.

Evidence of Benefits Counseling's Efficacy

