Data collection will be conducted at the Northampton VA Medical Center and the West Haven VA Medical Center. Veterans will complete baseline evaluations, and then be given a user ID and instructions to log-on to a study website at home to receive their randomization assignment. Only those who do so will continue in the study and be asked to complete the telephone-delivered assessments on weeks 4, 12, and 24. This randomization after logging in restricts participation to people who demonstrate some motivation and ability to access a website.

Sequence of procedures for the clinical trial:

- Potentially eligible Veterans scheduled for a Compensation examination are identified by reviewing Compensation clinic schedules and charts.
- Potentially eligible Veteran receives letter explaining that a study recruitment telephone call will be coming, thus allowing the Veteran to opt out of receiving it (see Appendix). Veterans can also opt out by calling a toll-free phone provided in the letter.
- Telephone call inviting participation. The Research Assistant calls and asks the Veteran questions to determine eligibility. Following a script (see Appendix), the Research Assistant describes the study to the Veteran and schedules an appointment for informed consent and data collection. Appointments will be scheduled before a Veteran's planned Compensation examination and up to 3 months after the exam. Veterans vary in how able they are to schedule appointments immediately before or after Compensation examinations. Flexible scheduling balances feasibility and experimental rigor.
- Informed consent and baseline data collection by Research Assistant.
- The Research Assistant gives the Veteran a user ID and password to log on to the study Website.
- Veteran goes home, logs onto the website, and receives directions to log-on to either the Benefits Counseling or Control websites (i.e. the Veteran is randomized).
- Veteran is called by the study therapist within two days of logging on and is counseled with the assigned treatment. If the Veteran has not logged on for randomization within a week, then the therapist will call and encourage the Veteran to log-on for randomization and continuation in the study. If after one more week the Veteran has not been randomized, that participant will be discontinued from the study.
- Assessments by phone at weeks 4, 12, 24 (only of randomized Veterans).

B. Remotely-Delivered Benefits Counseling

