Session One: Your Benefits and Your Goals	To engage Veteran in the program, explain that Veterans can work and earn service-connection	
 -Instruction on how to use the website and its purpose -Review Veteran's experience applying for benefits -Inquire about Veteran's perception of relationship between disability benefits and work, explanation of relationship between disability benefits and work
Session Two: Your Options-Work and Otherwise	To enhance the Veteran's motivation to work. Based on goals, make an Action Plan.	
 -Elicit situation, feelings and attitudes towards employment -Motivational Interviewing exercises (e.g., Decisional Balance, Values Card Sort) -Review barriers to work including the disabling condition; consideration of treatment for disabling condition -Develop an action plan
Session Three: After Your Service Connection Decision	To review the goals and plans identified in the previous sessions in light of the award (or denial) of service-connection benefits	
 -Inquiries about Veteran's reaction to service-connection decision; provide information about how to appeal decision -Reconsider work and financial goals (from Session Two) in light of service-connection award (or denial) -Review action plan

		-Troubleshoot barriers, summary, and follow-up resources
--	--	--

c. The relationship between work and benefits is explained using graphics, and video testimonials from Veterans who are service-connected and work.

C. Control Condition:

1. Description of the Control Condition and Rationale for Choosing this Specific Control Condition: This control condition, involving referral to VA websites, represents enhanced treatment-as-usual. A Veteran who completes a Compensation examination ordinarily has no further treatment or referral as part of the Compensation examination. The information about benefits-related websites controls for having information available about benefits and receiving encouragement to pursue that information.

2. Control Condition Content: The control condition involves being urged to explore links to three VA websites with Compensation & Pension-related information:

- a. The VBA website with links about VA disability compensation. The questions answered are: What is VA Disability Compensation?, Who Is Eligible?, How Much Does VA Pay?, How Can You Apply? And Upcoming Events.

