1. Separation of Therapies from Assessments: Veterans will be instructed not to tell the Research Assistant if they are receiving Benefits Counseling or not. To determine if the blind was maintained, we will ask the Research Assistant to rate the condition each Veteran was assigned to and the Research Assistant's certainty about the assignment on a 0-100 visual analogue scale.

2. Participant Tracking Procedures: After randomization, participants will schedule phone assessments with the Research Assistant. The Research Assistant will offer to place reminder calls or a text message/email reminder prior to the assessment call to help Veterans remember them. Within two days of an upcoming appointment, participants will receive a reminder call/email/text. (Sample text/email would read: "You have a follow-up phone call for the VA research study scheduled for [date] at [time]. Please call [Research Assistant's name] at [phone number] if you need to reschedule. Do not reply to this message as the account is not monitored. Thank you.") If a participant misses a scheduled assessment, the Research Assistant will place follow-up calls.

To the extent that participants are not able to be reached for either the phone assessments (or therapist telephone calls), participants' VA medical records will be accessed to obtain updated telephone numbers, in addition to updated resident addresses. This will allow us to call participants and send letters to participants using the most up to date information on file. We also will seek to obtain information from participants' VA records regarding upcoming appointments and additional locations where they can be located so as to re-establish contact. Participants will have the option to not allow this via an opt-out statement included in the consent form.

Through these proposed means we believe we will be able to increase participant retention and better track the outcome of participation in the current study.

3. Schedule of Assessments

Visit	Domain	Assessment
BL	Characterize Participants	Baseline Questionnaire, SF 36; Alcohol, Smoking and Substance Involvement Screening Test (ASSIST); Disability Application Appraisal Inventory; PTSD Checklist (DSM5 version); Brief Symptom Inventory
BL, 4, 12, 24	Baseline and Outcomes	Timeline Follow-Back Calendar: paid work, unpaid work, voc rehab, education; Income from different sources; Brief Symptom Inventory; PTSD Checklist-5

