2. The SF-36 will be used to measure self-rated quality of life. The SF-36 was derived from the Medical Outcomes Study to assess health-related quality of life [51]. Patients answer 36 questions about health related impairments in daily activities, impairments from illness, and psychological states.

3. Alcohol, Smoking and Substance Involvement Screening Test (ASSIST): The ASSIST consists of eight questions concerning use of alcohol and or drugs, mostly within a three-month timeframe. It includes inquiries about amount of use, and incorporates questions that are somewhat indirect such as whether anyone else asked the Veteran to cut-down on use [60]. The ASSIST has excellent reliability [61] and validity [62].
4. The Disability Application Appraisal Inventory [28] was developed to better understand VA disability claimants' views of disability application and the role the beliefs play in clinical presentation. It is composed of 3 scales assessing (i) understanding of the claims process (Knowledge scale), (ii) expectations specific to the process (Negative Expectations scale), and (iii) the reasons becoming service connected is important to Veterans (Importance scale). The Disability Application Appraisal Inventory's test-retest reliability, internal consistency, factor structure and validation against selected MMPI subscales were tested and the measure has good reliability and construct validity [28].
5. The Post Traumatic Stress Disorder Checklist for DSM5 is a 20-item update [3] of the extensively validated earlier version [63], which had excellent agreement with comprehensive observer ratings [64, 65]. Veterans are asked to rate their agreement on a 5-point Likert scale with statements about how bothered the Veteran has been by each symptom in the past month, and the total score is the sum of the 20 item scores. The wording is general enough to rate PTSD symptoms related to Military Sexual Trauma as well as Combat Trauma and it has been sensitive to treatment effects in behavior therapy trials [66].

Outcomes Measured Repeatedly (Baseline, Weeks 4, 12, and 24)

1. Work and rehabilitative activities. A time-line-follow-back method will be used to determine whether and on what days the Veteran engaged in different work-related activities.

--- work for pay (in-kind compensation such as reduced rent is only counted when it is a formal arrangement)

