1. Determination of Study Outcomes: We list below the outcome measures whose scoring requires explication. Many of the scales' scoring is embedded in our earlier description of the measure.

a. Primary Outcome: The a priori definition of a primary outcome reduces the risk of Type I error. The number of hours paid work will be the primary treatment outcome. As noted previously, this includes work that is formal or under-the-table, and includes formal in-kind arrangements. It does not include days engaged in informal in-kind arrangements (housekeeping) or illegal activities such as gambling.

b. Secondary Outcomes: Secondary outcomes include each of the other work-related activities considered separately (unpaid work, attending school, engaging in vocational rehabilitation). Another secondary outcome is days engaged in any of the above work-related activities. This measure of work-related activities has a range of 0 to 28 in that each day is scored for whether any work-related activity was engaged in on that day as a dichotomous (0,1) value.

Dollars earned will be log-transformed (adding “1” to totals before transformation to allow calculation for veterans with no income) for outcome analyses if it is heavily skewed by outliers with high incomes.

c. Scoring of Clinical Measures.

- i. Psychiatric Symptomatology: The Global Severity Index from the Brief Symptom Inventory will be the main outcome from the BSI. The depression subscale will be scored too because of the association between depression and poor work function.
- ii. The SF-36 will be scored to yield standardized Mental Health and Physical Health Component Scores, with a mean of 50 and population standard deviation of 10. As noted earlier, the PTSD Checklist items are summed to yield a single score.
- iii. For the Work-Related Attitudes Scale, EFA will be conducted if it can be accomplished with the sample, i.e., if there is approximately a 10:1 participant:item ratio and item communalities are high [.6 or greater] after dropping any items with poor variability. If EFA is not feasible, we will analyze inter-item correlations and estimate internal consistency reliabilities to identify items that cluster together within a domain that reflect the perceived work-benefits relationship. A mean score of all items in this domain (or domains, if more than one is identified), will be generated.
- iv. The ASSIST yields an overall substance use severity score.

d. Process Measures

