2. Becoming upset while discussing traumatic events: There is a risk that individual Veterans will become upset by discussing their traumatic events during assessments or counseling. In practice, study-related adverse events in clinical trials involving PTSD assessments among Veterans have been very rare. Research assistants will emphasize that answering questions is voluntary and will allow Veterans to answer questions at their own pace and without duress.

3. Information from the counseling being told to participants' clinicians at the VA or to someone who reviews their disability application. The counseling is unlikely to impact the Veteran's disability application. The therapist will not volunteer any non-emergent information in the Veterans' chart or to other clinicians, as this is contrary to the voluntary, Motivational Interviewing stance that is integral to Benefits Counseling. The therapist will write a note in the Veteran's VA chart after any phone counseling indicating that the participant was in this research study and spoke to the therapist.

Nevertheless, the therapist is going to convey information to other VA clinicians if the Veteran indicates information during the therapy that requires emergency intervention. If the Veteran indicates information suggesting imminent danger to the Veteran or to others, the Benefits Counseling therapist will share this information with other VA clinicians so they can take appropriate action. Therefore, Veterans will be told the risk that information that they tell the study therapist may be told to their VA clinicians and would then become available to someone who reviews their disability application. It is very unlikely that an emergency disclosure would prevent receipt of service-connected disability.

4. Potential effect of work on the benefits application process: Veterans compensated for physical or mental problems that developed during or were made worse by military service are not supposed to be penalized for coping well with these problems by working. However, the Veterans Benefits Administration reviews claims on a case-by-case basis, and it is unknown to what extent working will influence any individual Veteran's disability determination process. Veterans will be told this as part of the informed consent process.

5. Breach of Confidentiality: The website will not contain any PHI.

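### Paid hours are self-reported with no records check, and only the counseled arm is taught that work and benefits are compatible, so a one-arm rise in disclosure could add to the primary effect

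*Combined protocol and SAP*

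**What the plan says.** **Outcome and source.** Data Analysis, 1.a states: "The number of hours paid work will be the primary treatment outcome". It adds that "this includes work that is formal or under-the-table, and includes formal in-kind arrangements". The source is given under Outcomes Measured Repeatedly, item 1: "A time-line-follow-back method will be used to determine whether and on what days the Veteran engaged in different work-related activities". The Research Assistant takes the calendar at the baseline visit (Study Design Overview: "Informed consent and baseline data collection by Research Assistant") and by phone at weeks 4, 12 and 24 (Participant Tracking Procedures: "After randomization, participants will schedule phone assessments with the Research Assistant"). End of Study Measures take diagnoses, the award and VA service use from records. No wage, tax or employer record is named for hours or income.

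**Timing.** The baseline visit may fall before the Compensation examination or up to three months after it. The Session-Three call schedule provides for claims still undecided at weeks 12, 16 and 20.

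**What differs by arm.** Background gives "the perception that beneficiaries who work will definitely lose their disability benefits" as one reason that people on disability payments are underemployed. A goal of Session One is to "explain that Veterans can work and earn service-connection". The therapist table under Control Condition assigns vocational issues to the Benefits Counseling therapist only. Hypothesis 2A(ii) lists a larger fall in the belief that work and service connection are linked among the expected effects of assignment.

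**Safeguards.** Veterans are told not to reveal their arm to the Research Assistant, and Protection of Participants, item 1 makes research information confidential.

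**The concern.** The person who supplies the primary outcome knows what he or she was taught, and the teaching concerns the consequences of working while on benefits. Suppose some Veterans in both arms hold back part of their paid work at baseline. If counseling later makes them more open, reported hours rise in that arm and not in control. Baseline reports precede counseling, so the change would appear after baseline in one arm. That is a treatment-by-time interaction, the same contrast as the primary hypothesis. A positive result could then be partly a change in reporting, and the plan has no analysis that would show it.

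**Working it through.** **Inputs from the Precision Analysis:** 52 per arm; standardized slope difference 0.40 with 95% CI (.01, .79); 40 hours per 28 days at baseline; no change in control; 6% growth per month; 43%, or about 17 hours, by month 6. **Assumed, not in the documents:** every concealment rate below.

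**1. The plan's own figures reproduce.**
- SE = √(2/52 + 0.40²/(4×52)) = 0.198. CI = 0.40 ± 1.96×0.198 = (0.012, 0.788), which rounds to (.01, .79).
- exp(0.06×6) − 1 = 43.3%, and 40×0.433 = 17.3 hours.

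**2. Illustration: disclosure grows steadily to month 6.** True work is held at 50 hours per 28 days in both arms. With 20% concealed at baseline, reported hours are 50×0.80 = 40, the plan's figure. Control stays at 20%.
- Counseled arm falls to 10% concealed: 50×(0.90 − 0.80) = 5 hours, and 5/17.3 = 29%.
- Counseled arm falls to 0%: 50×(1.00 − 0.80) = 10 hours, and 10/17.3 = 58%.

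On the plan's standardized scale, the implied SD of the monthly log-slope is 0.06/0.40 = 0.15. The spurious effect is ln(ratio of reporting shares)/6/0.15:
- ln(0.90/0.80)/0.9 = 0.13
- ln(1.00/0.80)/0.9 = 0.25

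With SE = √(2/52) = 0.196, the chance of p < .05 with no change in true work is 10% and 24% respectively, against a nominal 5%.

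**3. Illustration: disclosure changes early.** Counseling calls begin at weeks 1 and 2, so a step complete by week 4 is at least as plausible. For assessments at weeks 0, 4, 12 and 24 with equal weight, the mean time is 10 and the deviations are −10, −6, 2 and 14.
- Sum of squares: 100 + 36 + 4 + 196 = 336.
- A unit step at weeks 4, 12 and 24 gives a numerator of −6 + 2 + 14 = 10.
- The slope is 10/336 per week; over 24 weeks it is 24×10/336 = 0.71 of the step.
- 5×0.714 = 3.6 hours, and 3.6/17.3 = 21%.
- 10×0.714 = 7.1 hours, and 7.1/17.3 = 41%.

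**4. Can the plan tell more work from more disclosure?**
- *Research Assistant blinding* limits assessor bias. The reporting Veteran is not blind.
- *Confidentiality* applies to both arms. It may lower concealment overall but does not remove a difference that counseling creates.
- *The mediator analysis* relates the slope of the work-benefits belief to the slope of hours. The two would be correlated under either explanation.
- *Income* is listed among the participant assessments with no records source, so it is not an independent check.
- *The ancillary quadratic analysis* could show an early change, but an early real gain in work would look the same.

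**The case against.** The strongest reply is that the key link is not in the documents. Background says the belief keeps people from working; it does not say that Veterans hide work from researchers. A reader might infer that concealment is an established fact here, and that inference is not supported.

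A reader might also infer from Risks and Discomforts, item 3 that calendar answers can reach the claim file, because it warns that information "would then become available to someone who reviews their disability application". In context, the warning concerns emergency disclosures made to the therapist. The calendar goes to the Research Assistant, and the stated limits on research confidentiality are suicidality, homicidality and abuse of a minor. Hours worked are not among them. At most, the warning bears on how safe a Veteran feels.

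The contrast between arms may also be smaller than it looks. Item 4 of the same section says Veterans should not be penalized for working, then that the effect on an individual claim is unknown, and that this is explained at consent. Depending on how much of the paragraph that covers, both arms may hear part of the message before randomization. Some claims will be decided before week 24, which could weaken the motive to conceal in both arms.

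Finally, the full calendar code list is not shown, so it may already distinguish types of paid work. These points all stand. They reduce the likely size and certainty of the bias, but none gives the plan a way to detect it.

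**Conclusion.** The point holds as a possibility that the plan can neither exclude nor detect, not as a demonstrated bias. Under the assumed fall in concealment from 20% to 10% or 0% in the counseled arm alone, the artefact is 5 to 10 hours (29% to 58% of the planned effect) if disclosure rises steadily. It is 3.6 to 7.1 hours (21% to 41%) if the change is complete by week 4. Both ranges assume constant true work, no change in control reporting and, for the step, equally weighted assessments.

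A reader might infer that the whole planned effect could be artefact. That needs a different and more extreme scenario: about 57 true hours with 30% concealed at baseline (57.3×0.70 = 40 reported), moving to full disclosure in one arm only. Nothing in the documents supports a rate of that size. The precision calculation itself is sound. The change below is a cheap improvement, not the correction of an error.

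**What to change.** 1. Before every calendar, including baseline, have the Research Assistant read one fixed sentence in both arms. It should say that calendar answers are confidential research data and are not sent to the benefits office, in line with Protection of Participants, item 1. Starting at baseline matters, because the aim is to lower concealment in both arms before counseling begins.
2. Record paid work as payroll/formal (including formal in-kind arrangements) or under-the-table, if the calendar does not already do so. Keep the primary outcome as defined. Pre-specify the primary model repeated on formal hours as a sensitivity analysis and report both results. If the effect is confined to under-the-table hours, name differential disclosure as one possible explanation. Do not rule such an effect out as real work, since the plan deliberately counts those hours.

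The cost is a few seconds per call, possibly one calendar code, and one extra analysis. The check is partial, because formal hours can also be under-reported.
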